2.1. PRIMARY OBJECTIVE

To compare “Combidex” Nanoparticle-Magnetic Resonance Lymphography (Nano MRL) and 68Ga-PSMA positron emission tomography (PET) to the gold standard and current practice; the histology of pelvic lymph node dissection, to locate the position of lymph nodes

2.2. SECONDARY OBJECTIVES

Determine whether concordance of these two imaging technologies (68Ga-PSMA PET - functional imaging, and Nano MR - anatomical imaging) is worse, better or equal to lymph-node dissection.

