1.1. DISEASE BACKGROUND

Following curative intended therapy in prostate cancer patients, a high proportion of patients (approx. 25%) relapse with local and/or distant recurrence [1]. The metastasis of a lymph node (LN) in a patient with prostate cancer means that the disease has become systemic with the increased risk of disease progression. Therefore the ability to detect the presence of LN metastasis is important in terms of disease prognosis and treatment selection. In the past, patients with LN metastasis have had poor prognoses due to the scarcity of accurate staging techniques and toxic treatment regimens such as radiotherapy. For those patients with a medium to high risk of having LN metastasis, the current procedure is a bilateral pelvic lymph node dissection (LND). It is generally accepted that a LND provides important information for prognosis which cannot be matched by other current procedures. Therefore, it is the standard procedure prior to curative treatment with either radical prostatectomy or radiation therapy. Besides being a staging procedure, pelvic LND may be curative, or at least beneficial, in a subset of patients with limited lymph node metastases [2, 3]. The number of nodes removed during LND has been significantly correlated with the time to progression [3, 4]. However, results from ongoing prospective studies are awaited. On the other hand, the LND is not optimal due to the frequent inability to remove all suspicious lymph nodes within the dissection area. 41% of metastatic LN disease is not found [5], due to these LN being outside the routine surgery field. As a result, many urologists will perform an extended lymphadenectomy (e-LND), which leads to extended operating times and the risk of complications [6]. Also, radiotherapy of LN metastases has limitations: more than 50% of metastatic LN are outside the routine (RTOG-CTV) radiation field [7]. As a result, the effect of standard salvage LN radiotherapy is limited [8]. Currently used imaging techniques such as CT and conventional MRI are not sensitive enough to detect prostate cancer metastases due to the small size of the nodes (< 8mm) [9]. Finally, 11C-Choline PET/CT fails to detect metastatic LN, when they are smaller than 6 mm since a minimum amount of tracer needs to be present in the LN to be detected [10].

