Following the infusion, the participants will be observed for one hour before being allowed to return home. The risk management of the infusion are described in item 5.3. In the next 2 to 3 days, the participants will be referred to have a MRI at Medscan Bangaroo. All Nano MRL scans will be double assessed by two experienced readers (one at I-Med Radiology and the other at The Wesley Hospital) and then by an experienced reader of Radboud University Nijmegen, the Netherlands.

The assessment of Nano MRL and 68Ga-PSMA PET scans represents a crucial endpoint in this study. Consequently, before the start of the trial we will define imaging standards and provide an intensive training of image interpretation. In order to ensure a homogeneous high quality of image assessment according to the requirements of MAGNIFI Trial, extensive effort will be made for training, including a 10 days training at the Radboud University Nijmegen the Netherlands. To assure the quality of this training, each investigator judging the images in the MAGNIFI Trial will have to pass a certification.

3. *Radical prostatectomy with pelvic lymph node dissection*

Patients will undergo radical prostatectomy and extended pelvic lymph node dissection, as clinically indicated within 7-10 days following Combidex nano-MRL imaging, with all dissected lymph node packets being dissected and labelled. Suspicious lymph nodes detected on nano-MRL or PSMA will be specifically targeted for resection during lymph node dissection.

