After dissection, the specimens will be sent to pathology for histopathological examination. The lymph nodes will be reviewed at 2mm dissections. The result of histological examination of the lymph nodes (gold standard) will be compared with the result of 68Ga-PSMA PET scan and Nano MRL. Sensitivity, specificity, positive predictive value (PPV), and negative predictive value (NPV) for Nano MRL and Ga68-PSMA PET scan in pelvic lymph nodes with corresponding CT size measurement in comparison with histopathology will be assessed for detection of lymph node metastases.

Analysis will include assessing sensitivity, specificity, diagnostic accuracy, positive and negative predictive values for different levels of Nano MRL and PSMA PET avidity in pelvic lymph nodes with corresponding CT size measurement in comparison with histopathology.

5. *Re-imaging*

In participants where the 68Ga-PSMA PET and/or Nano MRL detected metastases in the lymph nodes but these were not seen in the histopathology (i.e., a false positive result), the participant will undergo a repeat PSA test, a 68Ga PSMA PET scan and a Nano MRL 6 weeks after the radical prostatectomy to confirm the accuracy of the original results and to ensure that no other sites of metastases missed. As noted in section 5.3, correspondence from [name] (Appendix D) and from clinical evidence to date, there have been no safety issues as a consequence of having a repeat 68Ga PSMA PET scan and/or a Nano MRL. All precautionary safety measures will be performed.

6. Follow up visits

As part of the participant's clinical care, follow up consultations with the treating urologist are planned for 6 weeks, 2 months, 6 months, 12 months and 24 months post surgery.

7. Quality of Life (QOL) survey

To determine the outcome of treatment, the participant will be asked to complete the self-reporting Expanded Prostate Cancer Index Composite (EPIC) survey. The EPIC survey has been extensively used to report on the physical, emotional and psychological outcomes of the prostate cancer patients. The participant will ask to complete the survey at baseline (prior to surgery), at 6 weeks, 3 months, 6 months, 1 year and then yearly for a minimum of 5 years.

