δ is the difference in the proportions of the two types of discordant pairs: (B-C)/ (N×n)

n = number of observations per patient (6)

For the calculations, it was additionally assumed that the proportion of positive packets was 0.15, φ = 0.10, and δ = 0.04. This assumes the following proportions:

[figure not shown]
| Combined Test | Histology | | Total |
|---------------|-----------|----------|-----------|
| | Positive | Negative | |
| Positive | 0.12 | 0.07 | 0.19 |
| Negative | 0.03 | 0.78 | 0.81 |
| Total | 0.15 | 0.85 | N×n = 480 |

Gonen M. Sample size and power for McNemar's test with clustered data. *Statistics in Medicine* 2004, 23: 2283-2294

b) Statistical Analysis:

We will compare 'packet concordance rate' between histology and MR Lymphography using a MRA arterial map (that can be acquired at the MRL) to locate the position of the lymph node, the 68Ga PSMA PET SCAN plus a combined evaluation, and histology. As indicated in the diagram below, lymph nodes are removed by one lump of fat (region-packet) at a time (refer to region-packets 'a' to 'f' in figure below). The two tests (MR lymphography and 68Ga PSMA PET) will indicate (with error)

whether each node is positive or not, and thus whether each region-packet is positive (at least one node positive) or not (no nodes positive). The combined evaluation is a consensus of the two tests: region-packets are positive if one or both tests indicate positive and negative only if both tests indicate the region-packet is negative. Using histology, we can assess the accuracy of the two tests (plus combined evaluation) in terms of false positives.

| | Histology | MR Lymphography | Ga68 PSMA | Imaging Consensus |
|---|-----------|-----------------|-----------|-------------------|
| a | Negative | Negative | Negative | Negative |
| b | Positive | Positive | Positive | Positive |
| c | Negative | Positive | Positive | Positive |
| d | Negative | Negative | Negative | Negative |
| e | Positive | Positive | Positive | Positive |
| f | Positive | Negative | Negative | Negative |

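### Secondary objective 2.2 asks whether combined imaging is better than lymph-node dissection, but dissection histology is the reference standard, so the planned packet analysis cannot return that answer

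*Protocol*

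**What the plan says.** **The objective.** Section 2.2 of the protocol, repeated as objective 2 of the synopsis, asks whether the concordance of 68Ga-PSMA PET and Nano MRL "is worse, better or equal to lymph-node dissection". Read literally, this sets agreement between two scans against an operation. I take it to mean the combined imaging evaluation defined in section 7(b).

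**The reference standard.** Four places make dissection histology the truth:
- Section 2.1 compares imaging "to the gold standard and current practice; the histology of pelvic lymph node dissection".
- Section 5.2, item 4: "The result of histological examination of the lymph nodes (gold standard) will be compared with the result of 68Ga-PSMA PET scan and Nano MRL".
- Section 5.2, item 5, covers metastases reported on imaging where "these were not seen in the histopathology (i.e., a false positive result".
- Section 7(b): "Using histology, we can assess the accuracy of the two tests (plus combined evaluation) in terms of false positives".

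**The dissection.** Section 5.2, item 3, describes a fixed template of about six packets per man, each flagged as complete or incomplete. It adds: "Suspicious lymph nodes detected on nano-MRL or PSMA will be specifically targeted for resection during lymph node dissection". Some of these nodes may lie outside the template.

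**After surgery.** Under section 5.2, item 5, when imaging is positive and histology negative, "the participant will undergo a repeat PSA test, a 68Ga PSMA PET scan and a Nano MRL 6 weeks after the radical prostatectomy". Step 10 of the synopsis study procedures instead repeats both scans whenever they disagree with histology, within 6 to 8 weeks, and does not mention PSA. Re-imaging is diagnostic endpoint 1(d) in the synopsis. Section 7 mentions neither re-imaging nor PSA.

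**The concern.** The same dissection is both the comparator and the truth. A comparator judged against itself makes no errors, so every disagreement is charged to imaging and one of the three answers the objective offers is unavailable.

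This matters because sections 1.1 and 1.2 justify the trial partly by disease that dissection leaves behind. If imaging correctly detects a metastasis that surgery or sectioning missed, the planned analysis records a false positive. A reader who takes section 2.2 at its word could then read a shortfall against histology as an answer to a three-way question, when the analysis could give only two of the three answers.

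**Working it through.** **1. The plan's own figures.** The section 7 planning table gives these proportions of packets:

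| Combined imaging | Histology + | Histology − |
|---|---|---|
| Positive | A = 0.12 | B = 0.07 |
| Negative | C = 0.03 | D = 0.78 |

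The stated inputs reproduce: φ = B + C = 0.10, δ = B − C = 0.04, prevalence = A + C = 0.15.

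**2. Accuracy with histology as truth.**
- Imaging sensitivity = A/(A + C) = 0.12/0.15 = 80.0%.
- Imaging specificity = D/(B + D) = 0.78/0.85 = 91.8%.
- Dissection: 100% on both, by construction.

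The difference, imaging minus dissection, cannot exceed zero. The two-sided McNemar test does not change this: B > C says only that imaging calls more packets positive than histology does, and with histology as truth those extra calls are errors.

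**3. Size of the disputed cell.** 0.07 × 480 = 33.6 packets; 0.07 × 720 = 50.4 packets.

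**4. How the ranking depends on that cell.** Let a share f of cell B be real metastases that histology did not show. The protocol gives no value of f, so all values below are assumptions. With T = A + C + fB:
- imaging sensitivity = (A + fB)/T
- dissection sensitivity = (A + C)/T

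| f | Imaging | Dissection |
|---|---|---|
| 0 | 80.0% | 100% |
| 25% | 82.1% | 89.6% |
| 50% | 83.8% | 81.1% |
| 100% | 86.4% | 68.2% |

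Imaging overtakes when A + fB > A + C, that is f > C/B = 0.03/0.07 = 42.9%. This is more than 14.4 of 33.6 packets, or 21.6 of 50.4. Disease missed by both methods enters T for both and leaves the threshold unchanged.

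The threshold belongs to this table. Section 7(a) also names 95% sensitivity and 90% specificity. At 15% prevalence that gives C = 0.15 × 0.05 = 0.0075 and B = 0.85 × 0.10 = 0.085, hence a threshold of 0.0075/0.085 = 8.8%.

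**5. Whether the post-operative check fills the gap.**

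| | Synopsis, step 10 | Section 5.2, item 5 |
|---|---|---|
| Trigger | any disagreement with histology | imaging +, histology − only |
| Timing | within 6 to 8 weeks | 6 weeks |
| Measures | both scans | both scans and PSA |
| Men negative on both | not covered | not covered |

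Both versions repeat the index tests, so a persistent imaging artefact would look like confirmation. Section 7 gives no step by which the result reclassifies a packet or decides the objective.

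**The case against.** The strongest reply is that section 7 is an ordinary accuracy study, and the protocol already looks beyond histology. Re-imaging is a listed endpoint, with the stated purpose of confirming the original results and finding missed metastases. Packets are flagged when incomplete, which addresses surgical misses. How these are used may be set out in a statistical analysis plan that is not shown. On this view only the wording of one secondary objective is at fault.

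Much of that stands. The primary objective and the accuracy analysis are unaffected, and the following stronger readings, which a reader might infer, are not supported:

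- *The trial can never show imaging to be better.* Too strong. Re-imaging with PSA could give some evidence of disease left behind. It is selective and relies largely on the index tests, but it exists. The limit applies to the histology-referenced analysis.
- *The background's 41% can stand for f.* Section 1.1 says "41% of metastatic LN disease is not found [5], due to these LN being outside the routine surgery field". That is a share of metastatic disease lying outside a routine field. Cell B consists of packets that were removed and examined, in a trial using extended dissection. The denominators differ, so 41% neither estimates nor bounds f.
- *A worse result would be an artefact.* Cell C contains metastases that histology proved and imaging missed. Even if f were 41%, the planning table would still put imaging slightly behind on sensitivity (83.2% against 83.9%).
- *Image guidance makes the whole comparator depend on imaging.* The template packets are dissected whatever the scans show, so dependence is strongest for the additional nodes. Targeting should also lower f, because visible disease is less likely to be left behind.

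The reply does not remove the core point: the protocol itself fixes an objective that its own reference standard cannot answer in full.

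**Conclusion.** The point holds for the stated analysis. With dissection histology as truth, the section 7 packet comparison can find combined imaging worse than or at best equal to dissection. It cannot find it better.

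The disputed cell is 7% of packets under the planning table, about 34 of 480 or 50 of 720. Whether imaging is truly more or less sensitive than dissection turns on an unknown share of that cell. The threshold is 42.9% with the planning table and 8.8% with the 95% and 90% figures in the same section. Both rest on planning assumptions and on treating histology-positive packets as true positives. Neither predicts what the trial will find.

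The re-imaging rules do not close the gap. They differ between the synopsis and section 5.2, they leave out men negative on both imaging and histology, and section 7 does not use them to judge the objective.

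**What to change.** 1. Restate section 2.2 and synopsis objective 2 as agreement and diagnostic accuracy of the combined imaging evaluation against histology of a template dissection with additional image-targeted nodes. Remove *better* from what this comparison can conclude.
2. Report the re-imaging results separately, without merging them into the packet comparison.
3. Reconcile synopsis step 10 with section 5.2, item 5, on trigger, timing and measures.
4. Optionally, record PSA for every participant at the follow-up visits already planned, and compare PSA persistence or recurrence across the four imaging-by-histology patterns. Label this exploratory: PSA does not show where disease lies, and the groups drawn from 120 men will be small.

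Items 1 to 3 are text changes, and their price is a narrower stated claim. Item 4 adds one data field at existing visits. The packet analysis and the recruitment target stay as they are for this point.

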3. STUDY DESIGN

3.1. DESIGN

This study will be a prospective clinical trial, conducted by St Vincent's Hospital, Sydney, St Vincent's Prostate Cancer Centre, the Wesley Hospital, Brisbane, the Garvan Institute of Medical Research and the Radboud University Nijmegen, the Netherlands. Participant recruitment will occur at St Vincent's Hospital Sydney and the Wesley Hospital Brisbane. One hundred and twenty participants will be required, with 60 participants recruited from each recruitment site.

A trial management steering committee will be convened every six months to monitor the progress of the study. The committee will consist of members from each of the participating institutions.

3.2. STUDY GROUPS

There will only be one study group and it will consist of intermediate and high-risk cancer patients with a >10% probability on LN where LND would currently be performed as part of the treatment protocol (guided by the updated Briganti nomogram) [34]

3.3. NUMBER OF PARTICIPANTS

One hundred and twenty participants will be recruited over a two-year period; 60 participants will be recruited from St Vincent's Hospital, Sydney and 60 participants will be recruited from the Wesley Hospital, Brisbane.

3.4. NUMBER OF CENTRES

St Vincent's Hospital, Sydney (Participant recruitment)
The Wesley Hospital, Brisbane (Participant recruitment)
St Vincent's Prostate Cancer Centre (Participant recruitment)
The Garvan Institute of Medical Research/The Kinghorn Cancer Centre (Study management)
I-Med Radiology, Randwick

3.5. DURATION

This study is anticipated to run for 10 years. The first two years will be dedicated for participant recruitment while the subsequent years will be dedicated for participant follow-up and the completion of the Expanded Prostate Cancer Index Composite (EPIC Survey).

4. PARTICIPANT SECTION

4.1. INCLUSION CRITERIA

Patients must meet the following inclusion criteria to be eligible to participate in the study:

- Male, aged 18 years or over
- Confirmed adenocarcinoma of prostate and at least clinical stage T3A and/or Gleason sum $\geq 4+3=7$, or preoperative PSA ≥ 15 ng/ml and planned radical prostatectomy
- Suspected lymph node involvement pre- radical prostatectomy based on Briganti nomogram $\geq 10\%$.
- Suitable for radical prostatectomy and pelvic lymph node dissection, as per institutional guidelines and not yet treated pre-prostatectomy
- Subject is able to understand and willing to sign the participant information statement and consent form
- Subject is expected to remain available for 24 months of clinic visits

If patients do not meet the inclusion criteria, (e.g. PSA < 15) they can still receive the same treatment and go through the LND but they will not take part in the study.

4.2. EXCLUSION CRITERIA

[figure not shown]
Patients who meet any of the following exclusion criteria are not eligible to participate in the study.

- Previous treatment for prostate cancer (surgery, radiotherapy, chemotherapy, hormone androgen deprivation therapy)
- Secondary malignancy except skin cancer
- Proven metastatic disease
- Patients who refuse radical prostatectomy or pelvic lymph node dissection
- Patients who refuse to join the trial or are unable to consent
- Patients not being considered for further therapy
- Patient with previous pelvic surgery (e.g. bilateral hip replacement) that will limit the eLND
- Contra-indication to MRI scanning, IV iron infusion, allergy to dextran or other injectable contrast media used in this trial
- Patients who cannot lie still for at least 60 - 75 minutes or comply with imaging
- Unequivocal evidence of disease outside the pelvis on conventional imaging
- Subject has medical conditions that would limit study participation (per physician discretion)
- Subject is enrolled in one or more concurrent studies that would confound the study results of this study as determined by the study investigators
- Subject has a limited life expectancy that would not allow completion of 24 month visits

- Subject meets the exclusion criteria required by local law

5. STUDY OUTLINE

5.1. STUDY FLOW CHART

5.2. INVESTIGATION PLAN

1. Screening Procedures

Participants will be screened when they attend their first urology consultation for a radical prostatectomy following the diagnosis of prostate cancer. The participant will be intermediate and high-risk cancer patients with a $\geq 10\%$ probability on LN where LND would currently be performed as part of the treatment protocol (guided by the updated Briganti nomogram) [34]. All patients will have a clinical work-up in line with the current international guidelines for the treatment of high-risk prostate cancer including a pelvic MRI and routine bone scan. They will be assessed against the inclusion and exclusion criteria. Should they be deemed eligible for the trial, they will be provided with details of the trial and will be asked to participate by providing written consent.

2. Imaging

Participants who have consented to participate will then be referred to the St Vincent's Nuclear Medicine Department will have the following imaging services prior to surgery:

- 68Ga-PSMA PET scan
- Diagnostic CT (part of the 68Ga-PSMA PET scan)

In the event that a participant had a clinically indicated 68Ga-PSMA PET scan within 3 weeks at St Vincent's Hospital, the participant will not be required to have another scan. If the 68Ga-PSMA PET scan was performed elsewhere, the participant will be required to have one performed at St Vincent's Hospital for consistent reporting. The 68Ga-PSMA PET scan will be double assessed by two experienced readers at St Vincent's Hospital, Sydney and the Wesley Hospital.

At the return visit and prior to the surgery, Combidex, the imaging agent, will be administered to the patient at St Vincent's Hospital, Sydney. Combidex will be administered by a trained member of staff. Combidex will be administered by slow infusion over approximately 30 minutes following dilution in 100mls of normal saline. This method of administration minimises adverse events and allows the management of adverse should they occur by the halting the infusion. The protocol for Combidex Nano MRL infusion is found appendix C.

Following the infusion, the participants will be observed for one hour before being allowed to return home. The risk management of the infusion are described in item 5.3. In the next 2 to 3 days, the participants will be referred to have a MRI at Medscan Bangaroo. All Nano MRL scans will be double assessed by two experienced readers (one at I-Med Radiology and the other at The Wesley Hospital) and then by an experienced reader of Radboud University Nijmegen, the Netherlands.

The assessment of Nano MRL and 68Ga-PSMA PET scans represents a crucial endpoint in this study. Consequently, before the start of the trial we will define imaging standards and provide an intensive training of image interpretation. In order to ensure a homogeneous high quality of image assessment according to the requirements of MAGNIFI Trial, extensive effort will be made for training, including a 10 days training at the Radboud University Nijmegen the Netherlands. To assure the quality of this training, each investigator judging the images in the MAGNIFI Trial will have to pass a certification.

3. *Radical prostatectomy with pelvic lymph node dissection*

Patients will undergo radical prostatectomy and extended pelvic lymph node dissection, as clinically indicated within 7-10 days following Combidex nano-MRL imaging, with all dissected lymph node packets being dissected and labelled. Suspicious lymph nodes detected on nano-MRL or PSMA will be specifically targeted for resection during lymph node dissection.

After all imaging is complete, Patients will undergo radical prostatectomy and extended pelvic lymph node dissection, as clinically indicated, with all dissected lymph node packets being dissected and labelled. Approximately 6 packets of lymph nodes are expected per patients, each hemipelvis providing node packets from the external iliac vein, obturator fossa and internal iliac vessels as described by Bader et al. Specifically, all fibro-fatty tissue along the external iliac vein along the pelvic sidewall, caudal to the femoral canal and proximally to the bifurcation of the common iliac artery will be dissected and removed to be labelled as 'external iliac vein nodal packet'. All fibro-fatty tissue within the obturator fossa along the obturator muscle, skeletonising the obturator nerve and vessels will be labelled 'obturator fossa'. Finally the internal iliac artery and internal iliac vein will be skeletonised, all tissue removed from this dissection will be labelled 'internal iliac vessels'. Suspicious lymph nodes detected on nano-MRL or PSMA will be additionally targeted for resection during lymph node dissection, particularly presacral and mesorectal nodes. Specifically identified nodes in the mesorectal plane may be localised with percutaneous hookwire prior to dissection. At the discretion of the operating surgeons, and in consultation, suspicious nodes outside this template may also be resected if doing so does not place the patient at significant additional risk. Each nodal packet removed will also be qualified as either 'complete' or 'incomplete' for imaging vs histology concordance analysis. The reason for 'incomplete' dissection will be recorded.

An accredited robotic urological surgeon will perform the pelvic lymph node dissection. All participating urologists will undergo external video analysis and independent validation prior to commencement of the MAGNIFI trial.

4. *Histopathology*

After dissection, the specimens will be sent to pathology for histopathological examination. The lymph nodes will be reviewed at 2mm dissections. The result of histological examination of the lymph nodes (gold standard) will be compared with the result of 68Ga-PSMA PET scan and Nano MRL. Sensitivity, specificity, positive predictive value (PPV), and negative predictive value (NPV) for Nano MRL and Ga68-PSMA PET scan in pelvic lymph nodes with corresponding CT size measurement in comparison with histopathology will be assessed for detection of lymph node metastases.

Analysis will include assessing sensitivity, specificity, diagnostic accuracy, positive and negative predictive values for different levels of Nano MRL and PSMA PET avidity in pelvic lymph nodes with corresponding CT size measurement in comparison with histopathology.

5. *Re-imaging*

In participants where the 68Ga-PSMA PET and/or Nano MRL detected metastases in the lymph nodes but these were not seen in the histopathology (i.e., a false positive result), the participant will undergo a repeat PSA test, a 68Ga PSMA PET scan and a Nano MRL 6 weeks after the radical prostatectomy to confirm the accuracy of the original results and to ensure that no other sites of metastases missed. As noted in section 5.3, correspondence from [name] (Appendix D) and from clinical evidence to date, there have been no safety issues as a consequence of having a repeat 68Ga PSMA PET scan and/or a Nano MRL. All precautionary safety measures will be performed.

6. Follow up visits

As part of the participant's clinical care, follow up consultations with the treating urologist are planned for 6 weeks, 2 months, 6 months, 12 months and 24 months post surgery.

7. Quality of Life (QOL) survey

To determine the outcome of treatment, the participant will be asked to complete the self-reporting Expanded Prostate Cancer Index Composite (EPIC) survey. The EPIC survey has been extensively used to report on the physical, emotional and psychological outcomes of the prostate cancer patients. The participant will ask to complete the survey at baseline (prior to surgery), at 6 weeks, 3 months, 6 months, 1 year and then yearly for a minimum of 5 years.

